6.5 Concomitant Therapy

Throughout the study, investigators may prescribe any concomitant medications or treatments deemed necessary to provide adequate supportive care, including calcium supplements, phosphate binders, active vitamin D sterols, vitamin D supplements except for those listed in [Section 6.8](#). These medications will not be provided by Amgen.

Medication use at screening and then at every study visit including Early Termination will be recorded and categorized by general, vitamin D supplement, active vitamin D sterol, calcimimetics, calcium supplements, or phosphate binder. Dialysate calcium will be collected at screening and anytime there is a change. For previous cinacalcet use, specific reasons for discontinuation will be captured.

Concomitant therapies are to be collected in the eCRF from informed consent through the EOS. Therapy name, indication, dose, unit, frequency, route, start date and stop date should be recorded.

6.5.1 Calcium Supplements

Subjects receiving calcium supplements must have had no more than a maximum dose change of 50% within the 2 weeks prior to screening laboratory assessments and remain stable through randomization. Except during the screening period, calcium supplement therapy may be adjusted as needed based on Investigator clinical judgment.

6.5.2 Phosphate Binders

Subjects receiving phosphate binders must have had no more than a maximum dose change of 50% within the 2 weeks prior to screening laboratory assessments, remain stable through randomization, and be expected to maintain stable dose for the duration of the study except as defined in the protocol (see [Section 6.5.6.2](#)).

Changing the type of phosphate binder is discouraged during the study and should only occur if unavoidable (eg, drug shortage). Should a change in type of phosphate binder be required, equivalent doses should be prescribed to maintain stable clinical effects to the extent possible.

6.5.3 Active Vitamin D Sterols

Subjects receiving an active vitamin D sterol must have had no more than a maximum dose change of 50% within the 4 weeks prior to screening laboratory assessments, remain stable through randomization, and be expected to maintain stable dose for the duration of the study, unless a change in dose is appropriate and consistent with the guidance in this protocol.

However, changes to the dose of active vitamin D sterols are permitted by the Investigator for reasons of safety with respect to the management of increased or decreased cCa as defined in the protocol (see [Section 6.2.3.2](#) and [Section 6.5.6.1](#)).

Changing the type of active vitamin D sterol is emphatically discouraged during the study and should only be considered, if unavoidable under uncommon circumstances such as

drug shortage or drug availability. Should a change in type of active vitamin D sterol become necessary, equivalent doses should be prescribed to maintain consistent clinical and biochemical responses to the extent possible. The doses provided should be regarded as approximately equivalent doses to guide conversion between type and/or dosage form.

6.5.4 Nutritional Vitamin D

If prescribed by the individual Investigator, subjects may receive nutritional vitamin D (ergocalciferol [D₂] or cholecalciferol [D₃]) without restriction. Examples of nutritional vitamin D compounds are provided below:

- cholecalciferol
- ergocalciferol
- renal multivitamins that contain D2 or D3

6.5.5 Allowed Treatments and/or Procedures During a Study Period

- Subjects should be on maintenance hemodialysis treatment with a prescription for dialysis 3 times per week. Dialysis duration and membrane may be modified to maintain adequate hemodialysis treatment (eg, Kt/V \geq 1.2 or URR > 65%). If a subject requires a significant change in hemodialysis prescription to maintain adequate hemodialysis (eg, permanent change from TIW), then the subject will be discontinued from treatment with IP, and every effort will be made to continue to follow the subject through the duration of the study.
- Intermittent additional hemodialysis treatment (eg, for ultrafiltration) or changes in hemodialysis schedule (eg, missed/rescheduled treatments or shifts in schedule) are not considered significant changes in hemodialysis treatment prescription.
- Subjects must have a prescribed dialysate calcium concentration \geq 2.5 mEq/L (1.25 mmol/L) stable for at least 4 weeks prior to screening laboratories, and the dialysate calcium concentration must be maintained \geq 2.5 mEq/L (1.25 mmol/L) throughout the study.
- Medications used to treat hemodialysis-related symptoms or comorbid conditions should be reported as concomitant medications whenever administered to the subject.
- Medications administered at each dialysis session (eg, heparin, diphenhydramine) should be reported on the eCRF with a frequency of 3 times per week unless a change in dose or frequency occurs. The following medications used in the delivery of hemodialysis should not be reported on the eCRF as concomitant medication:
 - local anesthetic for cannulation
 - saline prime for the dialysis circuit
 - saline or hypertonic saline for management of intradialytic hypotension
 - oxygen

Approved

6.5.6 Management of Laboratory Values

6.5.6.1 Management of Elevated Serum Corrected Calcium or Symptomatic Hypercalcemia

The following guidance is provided for the management of serum cCa above the upper limit of the reference range. If a subject has 2 consecutive central laboratory cCa > 10.6 mg/dL (**2.64 mmol/L**), then doses of active vitamin D sterol, oral calcium intake, and/or dialysate calcium concentration may be reduced based on Investigator clinical judgment; however, dialysate calcium concentration must remain \geq 2.5 mEq/L (1.25 mmol/L), unless otherwise permitted by Amgen.

If a subject has a central laboratory cCa > 11.0 mg/dL (**2.74 mmol/L**) or develops symptomatic hypercalcemia, then any active vitamin D sterol and oral calcium intake (including calcium-based phosphate binders) may be reduced or discontinued, and dialysate calcium concentration may be reduced based on Investigator clinical judgment; however, dialysate calcium concentration must remain \geq 2.5 mEq/L (1.25 mmol/L). Common signs and symptoms of hypercalcemia include: nausea, vomiting or constipation, fatigue or weakness, musculoskeletal pain, hypertension, impaired concentration, confusion or lethargy.

6.5.6.2 Management of Serum Phosphorous

Serum P will be monitored locally in accordance with the dialysis unit's standard operating procedures during the study. It is recommended that phosphate binder dose remain stable throughout the study. At the Investigator's clinical discretion and based on dialysis unit routine monitoring tests, phosphate binder dose may be adjusted consistent with the following guidance:

- If 2 consecutive local predialysis serum P values are $>$ 5.5 mg/dL (**1.78 mmol/L**) and not amenable to modification via dietary counseling, then the dose of phosphate binder may be increased.
- If 2 consecutive local predialysis serum P values are $<$ 3.0 mg/dL (**0.97 mmol/L**), then the dose of phosphate binder may be decreased.

6.6 Medical Devices

The following medical devices for the IV infusion of IP (eg, inline filters, IV administration set, infusion pump) will not be provided by Amgen, as routine hemodialysis tubing should be used. The Investigator will be responsible for obtaining supplies of these devices.

Other medical devices, which are not considered test articles, may be used in the conduct of this study as part of standard care (eg, syringes, sterile needles, alcohol prep

pads). These devices that are commercially available are not usually provided or reimbursed by Amgen (except, for example, if required by local regulation). The investigator will be responsible for obtaining supplies of these devices.

6.7 Product Complaints

A product complaint is any written, electronic or oral communication that alleges deficiencies related to the identity, quality, durability, reliability, safety, effectiveness, or performance of a drug(s) or device(s) after it is released for distribution to market or clinic by either Amgen or by distributors and partners for whom Amgen manufactures the material.

This includes any drug(s) or device(s) provisioned and/or repackaged /modified by Amgen. Drug(s) or device(s) includes IP.

6.8 Any Product Complaint(s) Associated With an IP(s) or Non-IP(s) or Device(s) Supplied by Amgen are to be Reported According to the Instructions Provided in the IPIM Excluded Treatments, Medical Devices, and/or Procedures During Study Period

6.8.1 Excluded Treatments and/or Procedures During Study Period

The following treatments will be prohibited during the study:

- Treatment with commercial cinacalcet is prohibited during the study through the last study visit (ie, the 30-day follow-up visit). Treatment during the study with other medications known to be associated with hypocalcemia is strongly discouraged. Cinacalcet must not have been taken for at least 3 months prior to the first screening laboratory assessments.
- Use of grapefruit juice is prohibited during the study. Changes in medications, including herbal medications, that are strong inhibitors or inducers of the enzymes CYP3A4 and CYP1A2 (eg, erythromycin, clarithromycin, ketoconazole, itraconazole) are permitted throughout the study at the Investigator's discretion. The investigator should monitor subject cCa closely if these medications are initiated, discontinued, or the dose is changed.
- Cinacalcet is a strong inhibitor of CYP2D6. Therefore, subjects receiving concomitant therapy with medications that are predominantly metabolized by the enzyme CYP2D6 and have a narrow therapeutic index (eg, flecainide, vinblastine, thioridazine, and most tricyclic antidepressants) should be monitored closely during initiation and titration of the IP. Please refer to the product insert for additional details.

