7.2.3 Treatment

Procedures will be completed during the 26-week treatment period at the times designated in the Schedule of Assessments ([Table 2](#)). Prior to enrollment, subject eligibility must be confirmed with screening procedures. Subjects satisfying eligibility requirements will be enrolled and randomized 1:1 to either etelcalcetide or cinacalcet into the 26 week treatment period and should receive the first dose of investigational product within 1 day of randomization. Randomization will be stratified by screening PTH level (< 900 pg/mL, \geq 900 pg/mL) (**< 95.40 pmol/L, \geq 95.40 pmol/L**), screening **central laboratory** serum cCa (\geq 9.0 mg/dL, < 9.0 mg/dL) (**\geq 2.25 mmol/L, < 2.25 mmol/L**) measured by the central laboratory, and country (China versus

non-China). The date of the first dose of IP is defined as day 1. Baseline assessments will be performed on the first day of dosing with IP (day 1). All subsequent study visits will be scheduled based on the day 1 date.

The IP is to be administered after all pre-dose assessments have been completed on day 1. Administration of IV IP is to be administered 3 times per week at the end of each hemodialysis session as specified in [Section 6.2.1](#). Assessments during the Treatment Period should be performed during the designated study week on the same hemodialysis treatment day of the week as the day dosing was started whenever possible. Oral IP should be taken by the subject with food at approximately the same time every day of the 26-week treatment period as described in [Section 6.2.2](#). Week 27 assessments should be performed on the day of the first hemodialysis treatment after the last dose of IP. Concomitant medications, adverse events, and serious adverse events must be collected at every study visit.

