7.2.4 Follow-up Visit

Subjects will complete the follow-up visit 30 days (\pm 3 days) after the last dose of IP. If a subject early terminates from IP or the study, the follow-up visit should also occur within 30 days (\pm 3 days) after the last dose of IP.

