### Efficacy Assessment Phase (EAP)

The period between Week 20 and Week 27, inclusive.

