### **6.3 Per Protocol Set(s)**

The Per Protocol Analysis Set (PPAS) is defined as all randomized subjects who have no major protocol violations (as defined below) and have at least one post-dose PTH value and had at least 16 weeks exposure of IP. Subjects with the following eligibility deviations will be excluded from the PPAS:

- Less than 18 years at screening
- Not receiving maintenance hemodialysis three times a week for at least 3 months
- Not meeting either calcium concentration or PTH eligibility criteria at screening
- Received cinacalcet within 3 months prior to screening or underwent a parathyroidectomy within 6 months prior to dosing
- Currently enrolling in another study or less than 30 days since ending another study
- Having known sensitivity to either cinacalcet or etelcalcetide

Moreover, subjects who have the following deviations during study period will also be excluded in this analysis set:

- Had parathyroidectomy or kidney transplant before EAP
- Received commercialized cinacalcet during the study
- Missed > 14 consecutive days of intravenous (IV) IP or oral IP, excluding the withholding of IP for protocol-specific reasons

For the subjects who undergo parathyroidectomy or kidney transplantation during EAP, only the PTH values before the surgery will be used.

Subjects in the PPAS will be analyzed according to randomized treatment assignment. PPAS will be used in the sensitivity analysis of the primary endpoint.

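### SAP 6.3 drops subjects from the per-protocol set for commercial cinacalcet taken after the last EAP PTH sample, up to about 4 weeks later, when it can no longer affect the endpoint

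*Protocol*

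**What the plan says.** SAP Section 6.3 ends its PPAS definition with a list of on-study deviations, introduced by "subjects who have the following deviations during study period will also be excluded in this analysis set". One item is "Received commercialized cinacalcet during the study". It carries no date limit.

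The same list treats surgery differently. The item there is "Had parathyroidectomy or kidney transplant before EAP". For a subject operated on during the EAP, the SAP keeps the subject and says "only the PTH values before the surgery will be used".

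Protocol Section 6.8.1 sets the span of the ban: "Treatment with commercial cinacalcet is prohibited during the study through the last study visit (ie, the 30-day follow-up visit". Protocol Section 3.5.1 calls that visit the end-of-study visit. SAP Section 5.1 ends the study for a subject at the last study assessment, and defines the EAP as "The period between Week 20 and Week 27, inclusive". Protocol Section 7.2.3 fixes the last EAP sample: "Week 27 assessments should be performed on the day of the first hemodialysis treatment after the last dose of IP". Protocol Section 7.2.4 sets the follow-up visit at 30 days (± 3) after the last dose.

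**The concern.** Membership of an analysis set should not depend on what a subject does after the endpoint has been measured. A subject who finishes 26 weeks of treatment, gives every EAP sample and then takes commercial cinacalcet before the follow-up visit has a valid week 20-27 PTH mean. The later use cannot alter it, yet the rule removes the subject. The surgery item shows that the SAP's authors tied at least one exclusion to whether the event could affect the EAP values. The cinacalcet item does not follow that logic, and no reason is given.

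Two things are at stake. Each subject caught by the rule is an evaluable PPAS subject lost for no analytical gain. And if starting cinacalcet after treatment were related to response, the PPAS would be selected on outcome. Readers of a non-inferiority trial look to the PPAS for agreement with the full analysis set (FAS).

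**Working it through.** **1. Scope of the exclusion.** The SAP item does not define its own time span. Protocol 3.5.1, Protocol 6.8.1 and SAP 5.1 all run the study to the follow-up visit, and nothing limits the item to the treatment period or the EAP. Protocol 6.5 collects concomitant therapies through end of study, so follow-up use will be in the data and a literal program will apply the exclusion.

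**2. Length of the window for subjects who complete treatment.** Inputs: follow-up at 30 ± 3 days after the last dose (Protocol 7.2.4); last EAP sample at the next dialysis (Protocol 7.2.3). On a 3-times-weekly schedule the next dialysis is taken as 2 or 3 days after the last dose (assumption).

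- Nominal: 30 − 2 = 28 days, or 30 − 3 = 27 days.
- Extremes: 27 − 3 = 24 days, and 33 − 2 = 31 days.

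First use can fall anywhere from just after the last EAP sample to that limit.

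**3. The plan's own figure, as background.** The documents give no figure on this point. The stated non-inferiority power (over 99%, 300 per arm, 58% vs 68%, margin 12%) reproduces: SE = √[(0.58×0.42 + 0.68×0.32)/300] = 0.0392; Φ((0.12 + 0.10)/0.0392 − 1.96) = 99.99%.

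**4. How large could selection be?** The documents give no rate of post-treatment cinacalcet use, so this is an illustration. Assumptions: 250 per arm otherwise eligible; restart rates r_N among non-responders and r_R among responders, the same in both arms, with r_N above r_R. For a true response rate p:

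- retention = p(1 − r_R) + (1 − p)(1 − r_N)
- PPAS rate = p(1 − r_R) / retention
- half-width = 1.96 × √[Σ PPAS rate × (1 − PPAS rate) / (250 × retention)]

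Example, p = 0.60, r_N = 20%, r_R = 5%: retention = 0.57 + 0.32 = 0.89; PPAS rate = 0.57/0.89 = 64.0%. For p = 0.48: retention = 0.456 + 0.416 = 0.872; PPAS rate = 52.3%.

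True rates 60% cinacalcet, 48% etelcalcetide (deficit equal to the margin). The last column is the chance that the PPAS interval falls wholly below 12 points, Φ((12 − difference)/SE − 1.96), with SE = half-width/1.96:

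| r_N / r_R | Lost, cinacalcet / etelcalcetide | PPAS rates | Difference | Half-width | False pass |
|---|---|---|---|---|---|
| none | 0 / 0 | 60.0 / 48.0 | 12.0 | 8.67 | 2.5% |
| 10% / 2% | 5.2% / 6.2% | 62.0 / 50.1 | 11.9 | 8.89 | 2.6% |
| 20% / 5% | 11.0% / 12.8% | 64.0 / 52.3 | 11.75 | 9.15 | 2.8% |
| 40% / 10% | 22.0% / 25.6% | 69.2 / 58.1 | 11.2 | 9.61 | 3.7% |

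Planning rates 58% cinacalcet, 68% etelcalcetide:

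| r_N / r_R | Difference (cinacalcet − etelcalcetide) | Expected upper 95% bound |
|---|---|---|
| none | −10.0 | −1.6 |
| 10% / 2% | −9.8 | −1.2 |
| 20% / 5% | −9.5 | −0.8 |
| 40% / 10% | −8.7 | +0.2 |

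At the planning rates, PPAS non-inferiority power stays at or above 99.5% throughout. In both settings the difference shrinks toward zero: this flatters etelcalcetide if it is truly worse and works against it if it is truly better.

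**The case against.** A reader might infer that the rule systematically removes non-responders and so biases the PPAS toward non-inferiority. The documents do not support that.

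- Protocol Sections 6.2.1.2 and 6.2.2.2 blind sites and subjects to central PTH and suspend routine local PTH monitoring. SAP Section 7.3 keeps the treatment blind until all subjects have completed. During follow-up nobody at the site is meant to know who responded, and taking the drug would breach an explicit ban.
- The restart rates above are assumptions. A 40% rate for a prohibited drug within about 4 weeks is an extreme case.
- The direction depends on the truth. At the planning rates the shift is conservative.

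It is also fair to say that use during follow-up breaches Protocol 6.8.1, so a per-protocol set that excludes it does not contradict the protocol. The rule is objective and prespecified, and SAP Section 8.4 finalizes the deviation list before unblinding. Nor does any decision rest on the PPAS. Protocol Section 10.5.2 calls it supplementary, and SAP Sections 6.3 and 9.5.1.2 make it a sensitivity analysis. The primary analysis and the testing sequence use the FAS, and the PTH-completer and last-value-carried-forward analyses do not apply this exclusion.

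All of this stands, and it limits the point to a minor one. It does not answer the narrow criticism: the breach occurs after the endpoint is complete, and the neighbouring surgery item already draws that line. Nor does the point extend to use before or during the EAP. For subjects who stop treatment early, the 30-day follow-up window can fall before or inside the EAP, where use could affect the endpoint.

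**Conclusion.** The point holds in a narrow form. For subjects who complete treatment, SAP 6.3 excludes those whose first commercial cinacalcet use falls after the last EAP PTH sample and before the follow-up visit, a window of up to 24 to 31 days. This rests on reading the study as running to the follow-up visit, on which the three cited sections agree, and on 2 to 3 days between dialysis sessions.

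For any subject so affected, the loss of evaluable data is certain and needless. How many there would be cannot be computed from the documents, and the number could be very small. Outcome-related selection is possible but not shown. Under the assumed restart rates it moves the difference by 0.1 to 0.8 points at 60/48 and by 0.2 to 1.3 points at 58/68, in both cases toward zero. It is anti-conservative only if etelcalcetide is truly worse. Sample size and the FAS primary analysis are unaffected. Priority: minor.

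**What to change.** In SAP Section 6.3, before unblinding, limit the exclusion to commercial cinacalcet received on or before the date of the subject's last EAP PTH sample. For a subject with no EAP sample, limit it to use on or before the end of week 27. The fallback is needed because the PPAS requires only one post-dose PTH value, so such a subject can otherwise be a member.

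Leave the prohibition in Protocol Section 6.8.1 unchanged and keep reporting later use as a protocol deviation. The cost is one line of SAP wording and one date comparison in programming, with no change to trial conduct and no protocol amendment.

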6.9 Pregnancy Prevention Requirements

Female subject of childbearing potential who is unwilling to use an acceptable method of effective contraception during treatment with IP through 3 months after the last dose of IP. Acceptable methods of effective birth control include not having intercourse (true sexual abstinence), hormonal birth control methods (oral, intravaginal, transdermal,

injectable, or implantable), intrauterine devices, intrauterine hormonal-releasing system, surgical contraceptive methods (vasectomized partner with medical assessment of the surgical success of this procedure or bilateral tubal ligation/occlusion), or 2 barrier methods (each partner must use one barrier method and the female partner must use spermicide with the barrier method. The male partner must use a condom and the female partner must choose either a diaphragm, OR cervical cap, OR contraceptive sponge. A female condom is not an option because there is a risk of tearing when both partners use a condom. The two-barrier is acceptable in countries where spermicide is not available). Females of non-childbearing potential:

- Female subjects not of childbearing potential are defined as any female who:
- Is post-menopausal by history, defined as:
 - Age \geq 55 years with cessation of menses for 12 or more months, OR
 - Age $<$ 55 years but no spontaneous menses for at least 2 years, OR
 - Age $<$ 55 years and spontaneous menses within the past 1 year, but currently amenorrhoeic (eg, spontaneous or secondary to hysterectomy), AND with postmenopausal gonadotropin levels (luteinizing hormone and follicle-stimulating hormone levels $>$ 40 IU/L) or postmenopausal estradiol levels ($<$ 5 ng/dL) or according to the definition of "postmenopausal range" for the laboratory involved.

OR

- Underwent bilateral oophorectomy OR
- Underwent hysterectomy OR
- Underwent bilateral salpingectomy

